# Guidelines for Preparing a Research Protocol

#### **Instructions:**

- You do not need to complete this document if you are submitting an *Application for* Exemption or Application for a Chart Review.
- Do not use this template if:
  - o Your study involves an FDA regulated product. In this case, use the *Clinical* Trial Protocol Template.
  - o Your study has a protocol from a sponsor or cooperative group. In this case, use the Protocol Plus.
  - O Your study is a registry or repository for data and/or samples, In this case, use Protocol Template – Registry Studies. .
- If a section of this protocol is not applicable, please indicate such.
- Do not delete any of the text contained within this document.
- Please make sure to keep an electronic copy of this document. You will need to use it, if you make modifications in the future.
- Start by entering study information into the table above, according to these rules:
  - o Protocol Title: Include the full protocol title as listed on the application.
  - o Investigator: include the principal investigator's name as listed on the application
  - o IRB Number: Indicate the assigned IRB number, when known. At initial submission, this row will be left blank.
- Once the table information in entered, proceed to page 2 and complete the rest of the form.

 $\checkmark$  Continue to next page to begin entering information about this study  $\checkmark$ 

Version Date: 7/26/2017 Page 1 of 19

#### 1. PREVIOUS STUDY HISTORY

Has this study ever been reviewed and rejected/disapproved by another IRB prior to
submission to this IRB?
No ☐ Yes – if yes, please explain:

#### 2. BRIEF SUMMARY OF RESEARCH

- The summary should be written in language intelligible to a moderately educated, non-scientific layperson.
- It should contain a clear statement of the rationale and hypothesis of your study, a concise description of the methodology, with an emphasis on what will happen to the subjects, and a discussion of the results.
- This section should be ½ page

This pilot study is a collaborative effort between Northwell Health Fertility and the Radiology Department to streamline the fertility evaluation process and reduce the burden of stress many fertility patients experience by eliminating an imaging examination which is painful and exposes the patient to potentially harmful radiation.

The aim of this study is to improve the workup of infertility by integrating the examination of structural abnormalities of the fallopian tubes and uterus into a single radiation-free ultrasound guided procedure, the sonohysterosalpingogram (sonoHSG). Confirmation of tubal patency is extremely important as approximately 25-35% of female infertility can be attributed to fallopian tube pathology.1 The current paradigm is to use two separate imaging exams; the hysterosalpingogram (HSG), a transvaginal procedure that uses radiation and iodinated contrast to visualize the fallopian tubes, and the sonohysterogram, a transvaginal procedure that uses ultrasound and saline to visualize the uterus. By using agitated saline, to produce air bubbles, fallopian tube visualization is optimized during the time of sonohysterogram (sonoHSG). We plan to also utilize a continuous saline-air device that may produce a technically superior sonoHSG.

As a result of this study, the Radiology Department and Northwell Health Fertility will work together to encourage, educate, and support physicians to promote the utility of sonoHSG as the first imaging examination for the infertility workup. Currently, our institution is not routinely utilizing the sonoHSG despite the advantages in safety, comfort, and convenience to the patient. We aim to effect a change in the current practice at our institution by increasing the knowledge and visibility of the sonoHSG by creating educational materials for referring physicians, and creating a pilot program that demonstrates the value and efficacy of the exam. SonoHSG can be performed concurrently at the time of the sonohysterogram at no additional cost to the patient.

We will enroll 30 patients from Northwell Health Fertility over the course of one

year. Measures of success will include concordance between sonoHSG and HSG in patients who receive both procedures, and patient surveys evaluating pain utilizing the pain scale. If sonoHSG proves to be efficacious, our future steps will be to educate referring physicians and patients about the utility of the examination using print materials and a grand rounds lecture. We will also measure the number of sonoHSGs ordered compared to HSGs for the evaluation of fallopian tube patency in order to evaluate if there has been a shift in the standard of care.

# 3. INTRODUCTION/BACKGROUND MATERIAL/PRELIMINARY STUDIES AND SIGNIFICANCE

- Describe and provide the results of previous work by yourself or others, including animal studies, laboratory studies, pilot studies, pre-clinical and/or clinical studies involving the compound or device to be studied.
- Include information as to why you are conducting the study and how the study differs from what has been previously researched, including what the knowledge gaps are.
- Describe the importance of the knowledge expected to result

Recently, studies have shown that the sonoHSG alone is as reliable as the traditional HSG for evaluating fallopian tube patency, with the benefits of eliminating radiation exposure and the use of potentially harmful iodinated contrast. SonoHSG is also less painful when compared to the HSG and by reducing the number of procedures from two to one, the risk of infection is reduced. Additionally, a single procedure will help to shorten the diagnostic process of infertility and expedite treatment. Indeed, several recent reports support the use of sonoHSG as a first line diagnostic test for the workup of infertility. Ultimately, this test will be safer, more comfortable, and less expensive for our patients. SonoHSG is a long sought for alternative for tubal patency in place of the old, yet still practiced, "gold standard" HSG. We believe this initiative will help our institution streamline time to treatment and diagnosis of tubal pathology while improving patient experience.

The results of the study will be significant in determining and possibly changing the standard of care procedure from HSG to sonoHSG. Currently, the first line examination for the evaluation of fallopian tube patency is the hysterosalpingogram (HSG). This test involves radiation exposure, the use of iodinated contrast, and is accompanied by significant patient discomfort secondary to painful cervical manipulation and at times violent uterine contractions. 4 Some patients also require a sonohysterogram (aka a "water ultrasound") to better evaluate the endometrial lining and to assess for polyps, scar tissue, fibroids, or congenital uterine anomalies that may prevent a successful pregnancy. This initiative will extend the diagnostic capacity of the sonohysterogram by utilizing air bubbles, via a continuous air saline device, to allow concurrent visualization of the fallopian tubes (sonohysterosalpingography). Prior studies have shown, and our experience confirms, that fallopian tube patency can be accurately confirmed by sonoHSG and results are concordant with the HSG.3

The Radiology Department and Northwell Health Fertility will work together to encourage, educate, and support physicians to promote the utility of sonoHSG as the first imaging examination for the infertility workup. Currently, our institution is not routinely utilizing sonoHSG despite the advantages in safety, comfort, and convenience to the patient. We aim to effect a change in the current practice at our institution by increasing the knowledge and visibility of the sonoHSG by creating educational materials for referring physicians, and

creating a pilot program that demonstrates the value and efficacy of the exam. SonoHSG can be performed concurrently at the time of sonohysterogram at no additional cost to the patient.

#### 4. OBJECTIVE(S)/SPECIFIC AIMS AND HYPOTHESES

- A concise statement of the goal(s) of the current study.
- *The rationale for and specific objectives of the study.*
- The goals and the hypothesis to be tested should be stated.

The specific aim of this study is to evaluate the feasibility of the sonoHSG for it to be determined as the standard of care. Additionally, this is to improve the workup of infertility by integrating the examination of structural abnormalities of the fallopian tubes and uterus into a single radiation-free ultrasound guided procedure, the *sonohysterosalpingogram*.

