#### Sample Size Justification

The proposed sample size of 30 is based on feasibility, availability of resources, and the study timeline and not on any formal statistical power calculations. Once we have determined the feasibility of the sonoHSG, we intend to proceed with a larger clinical trial and appropriately power that study with a larger sample size.

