# Primary Study Endpoint:

Concordance between sonoHSG and HSG results. The sonoHSG and HSG will be considered interchangeable if the level of agreement between them is >= 80%.

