#### Secondary Endpoint:

- Quantification of level of patient pain in regard to sonoHSG versus HSG

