#### 12. STATISTICAL ANALYSIS

- *Describe how your data will be used to test the hypotheses.*
- State clearly what variables will be tested and what statistical tests will be used.
- *Include sample size calculations.*
- If this is a pilot study, state which variables will be examined for hypothesis generation in later studies.

Standard methods for descriptive statistics will be used, such as means, medians, proportions, and their associated 95% confidence intervals.

Concordance of the results between sonoHSG and HSG will be calculated using Gwet's Agreement Coefficient (AC1). An AC1 of  $\geq$ = 0.80 will be considered successful concordance between the two measures.

A repeated measures analysis of variance (RM-ANOVA) model will be used to examine the effect of treatment (sonoHSG vs. HSG) on the pain measure. The model will include the order in which the treatments are performed and the interaction between order and treatment. If the interaction is not found to be significant, only the main effects of treatment and order will be analyzed.

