#### 16. WITHDRAWAL OF SUBJECTS

- Describe anticipated circumstances under which subjects will be withdrawn from the research without their consent
- Describe procedures for orderly termination

• Describe procedures that will be followed when subjects withdraw from the research, including partial withdrawal from procedures with continued data collection.

The study can be discontinued by the study investigators at any time. Such discontinuation will have no effect on standard patient care.

Subjects can withdraw from the study at any time.

Subjects may be excluded from study analyses due to missing data for one or more of the following reasons:

- Failure to complete both study procedures in the specified time period.
- Failure to complete the pain scale survey.

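### Feasibility is the stated aim and the condition for the larger trial, but no endpoint measures it, and both concordance rules can be met while many sonoHSG procedures fail

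*Protocol*

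**What the plan says.** Section 4 gives the purpose: "The specific aim of this study is to evaluate the feasibility of the sonoHSG for it to be determined as the standard of care". The Sample Size Justification in section 8 makes the next step depend on it: "Once we have determined the feasibility of the sonoHSG, we intend to proceed with a larger clinical trial".

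Section 10 lists one primary endpoint, "Concordance between sonoHSG and HSG results", with the rule "The sonoHSG and HSG will be considered interchangeable if the level of agreement between them is >= 80" percent. It lists one secondary endpoint, "Quantification of level of patient pain in regard to sonoHSG versus HSG". Section 12 offers general descriptive statistics with 95% confidence intervals, Gwet's AC1 for concordance and a repeated-measures ANOVA for pain. An AC1 of at least 0.80 "will be considered successful concordance between the two measures".

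Section 2 names the same two measures of success, concordance (among patients who have both procedures) and pain. It ties a different step to efficacy: "If sonoHSG proves to be efficacious, our future steps will be to educate referring physicians and patients". The goals in section 4 include assessing difficulties with the procedure, but no endpoint follows from that goal.

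Section 16 says subjects may be excluded from analyses because of missing data. One listed reason is "Failure to complete both study procedures in the specified time period". The data list in section 11 includes the results of both procedures. It has no item for a failed or unreadable study, or for the reason.

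**The concern.** The aim and the condition for the larger trial name one quantity, and the endpoints measure two others. Neither concordance nor pain counts how often a sonoHSG can be started, completed and read for both tubes.

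The exclusion in section 16 adds to this. A sonoHSG that could not be completed is the event a feasibility study most needs to count. Here it is classed as missing data and may leave the denominator. A sonoHSG that was completed but could not be read is not covered by that exclusion, and the protocol does not say whether it is discordant, missing or something else.

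What is at stake is the statement that feasibility has been determined. No figure in the plan would support or contradict it. The only numerical success rules are for concordance, and they can be met whatever the failure rate.

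**Working it through.** **No planned figure to reproduce.** The sample size of 30 (up to 50) is expressly not based on a power calculation, and no completion or failure rate is given. The check therefore asks whether both concordance rules can be met while many procedures fail.

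**Inputs from the protocol.** Enrolment of 30 (sections 2 and 8); agreement of at least 80% (section 10); AC1 of at least 0.80 (section 12); permitted exclusion of non-completers (section 16).

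**Assumptions.** The number of failed sonoHSGs is 8 or 15 of 30. Each woman has one binary reading (patent or occluded). There are two discordant completers, one in each direction. Failures are left out of the concordance analysis. The protocol gives none of these figures.

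**Formulas.** Observed agreement: po = concordant / completers. Chance agreement: pe = 2π(1 − π), where π is the mean of the two procedures' proportions read as patent. AC1 = (po − pe) / (1 − pe). Intervals are Clopper-Pearson.

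**Case 1: 8 of 30 fail, 20 of 22 completers concordant.**
- po = 20/22 = 0.909, so the 80% rule is met.
- No concordant occluded women: π = 21/22, pe = 0.087, AC1 = (0.909 − 0.087)/0.913 = 0.90.
- Nine concordant occluded women: π = 12/22, pe = 0.496, AC1 = (0.909 − 0.496)/0.504 = 0.82.
- AC1 is therefore 0.82 to 0.90 across this range, and the AC1 rule is met.
- Women with a usable concordant result: 20/30 = 67% (47 to 83%).
- Failure rate: 8/30 = 27% (12 to 46%).

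**Case 2: 15 of 30 fail, 13 of 15 completers concordant.**
- po = 13/15 = 0.867, so the 80% rule is met.
- Two concordant occluded women, so each procedure reads 3/15 = 20% as occluded: π = 0.80, pe = 0.32, AC1 = (0.867 − 0.32)/0.68 = 0.80 (0.804 before rounding). The rule is just met.
- Three concordant occluded women: π = 11/15, pe = 0.391, AC1 = 0.78. The rule is missed, so this case depends on prevalence.
- Women with a usable concordant result: 13/30 = 43%.

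**A limit on the illustration.** The result depends on few discordances. With 8 failures and 18 of 22 concordant, agreement is 82% and passes section 10. However, π then lies between 4/44 and 40/44, so pe is at least 0.165 and AC1 is at most (0.818 − 0.165)/0.835 = 0.78. That fails section 12.

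**Sensitivity of the AC1 rule to failures.** In a simulation of 40,000 runs with assumed true agreement of 95% among completers, the chance of AC1 reaching 0.80 was about 0.96 with 30 completers, 0.94 with 21 and 0.90 with 15. Losing half the women hardly moves it.

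**What the sample can say about completion.** At n = 30, 27 readable results give 90% (73.5 to 97.9%), and no failures give an upper limit of 11.6% on the failure rate. At n = 50, 45 readable results give 90% (78.2 to 96.7%).

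**The case against.** The strongest reply is that feasibility here means fitness to replace HSG as standard of care. Section 4 uses the word in that phrase, section 2 names concordance and pain as measures of success, and section 10 links 80% agreement to interchangeability. On that reading the endpoints do address the aim. The reading is possible, but the protocol never states it. Even then, whether a test can be used first line depends partly on how often it yields a result.

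Several further objections stand and limit the point:
- A reader might infer that the concordance analysis is restricted to successful procedures. The text does not fix this: the exclusion is permissive and does not cover a study that was completed but unreadable. An SAP not shown here could settle the scoring.
- A reader might infer that the larger trial will be triggered by agreement among completers. The protocol states an intention and gives no rule. The link is inferred because concordance carries the only success threshold.
- Procedural difficulties are a stated goal, complications are followed up by phone, the principal investigator reviews deviations and adverse events, and section 12 allows proportions with confidence intervals. Some completion information could be reported from these, but none of it is a defined endpoint or is given a threshold.

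An SAP could specify how failures are handled. It would not remove the mismatch between the aim, the endpoints and the condition for the next trial, because this protocol fixes all three.

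**Conclusion.** The point holds as a mismatch between aim and endpoints. Feasibility is the specific aim and the condition for the larger trial, yet it has no definition, measure or threshold. Women whose sonoHSG fails may be removed from the analyses that do exist.

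On the assumed figures, both success rules are met with 27% of procedures failing and 67% of women having a usable concordant result. At 50% failures they are still just met if about 20% of completers are occluded. These are illustrations under assumed failure and agreement rates, not forecasts. They require failures to be excluded, which the text permits but does not require.

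It would go too far to say that the trial cannot answer its question at all. Concordance and pain remain interpretable for the women who have both, and they bear on replacing HSG. What is missing is a defined figure by which feasibility could be judged. A pilot of this size can supply one with useful, if wide, precision.

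**What to change.** 1. **Section 10:** add a feasibility endpoint, the proportion of all women in whom sonoHSG was started who had a readable result for both tubes. Report it with an exact 95% confidence interval and a tabulation of reasons for failure.
2. **Section 11, data collection form:** add fields for completed (yes/no), readable for both tubes (yes/no) and the reason if not.
3. **Section 16:** state that women whose sonoHSG was started but failed or could not be read stay in this denominator, whatever is done for concordance. Report concordance alongside the proportion.
4. **Section 8, Sample Size Justification:** base the statement that feasibility has been determined on this proportion together with concordance, against a level the investigators set before enrolment.

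The cost is a few sentences and a short addition to the form. No procedure, visit or patient is added. The downside is that the headline figure may look less favourable, because failures are counted.

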#### The specific goals are:

- To demonstrate the utility of sonoHSG as a first line imaging examination in the workup of infertility.
- To streamline the workup of infertility by diagnosing tubal pathology at the time of sonohysterogram.
- To make the workup of infertility safer.
- To improve patient comfort.
- To assess the side effects and complications of and difficulties related to the procedure.
- To assess patient tolerance by using the Pain Scale.

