#### 11. RESEARCH PROCEDURES

- *Include a detailed description of all procedures to be performed on the research subject and the schedule for each procedure.*
- *Include any screening procedures for eligibility and/or baseline diagnostic tests*

- Include procedures being performed to monitor subjects for safety or minimize risks
- *Include information about drug washout periods*
- If drugs or biologics are being administered provide information on dosing and route of administration
- Clearly indicate which procedures are only being conducted for research purposes.
- If any specimens will be used for this research, explain whether they are being collected specifically for research purposes.
- Describe any source records that will be used to collect data about subjects
- Indicate the data to be collected, including long term follow-up

Patients will be presented with the study information at the point of contact at the fertility clinic. They will then be contacted via phone prior to their scheduled appointment. A detailed overview of the study will be presented as well as the consent form. Upon verbal agreement over the phone, the clinician and/or study coordinator will go over the consent process in person on the day of the scheduled visit. As part of this study, subjects will have both the HSG and SonoHSG performed consecutively. The HSG will be performed as part of standard of care and the sonoHSG will be performed as part of research. In order to reduce bias, the procedures will be randomized in REDCap before each subject's scheduled visit. The clinicians will be blinded to the results of each procedure until both procedures have been completed.

The pain scale will be administered verbally immediately after each procedure by the technician/other study personnel in the procedure room.

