#### Schedule of Events:

	Pre-Visit	Visit 1	Follow-Up Visit (1-3 weeks)
Recruit Subject	X	X	
Evaluate Eligibility	X	X	
Initiate Informed Consent	X	X	
Obtain Written Informed Consent		X	
Collect Demographic Information		X	

HSG and sonoHSG (order decided via randomization)	X	
Administer the Pain Scale Survey (following each procedure)	X	
Follow-up with subject via phone to assess any complications/infections		Х

The procedures that would account as being research are obtaining informed consent, administering the pain scale surveys, performing the sonoHSG and the follow-up phone call.

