#### Data to be collected/obtained

The Data Collection Form will be completed for each enrolled patient. The data collection form contains the following categories of information to be collected/obtained for each subject:

- Patient record demographic data
- Patient record data on pre-existing co-morbid conditions or underlying disease
- Results of HSG and SonoHSG
- Response to evaluation survey with pain scale

The information that links the subject ID with the PHI (the Coded Identifier List) will be kept in the PI's locked office and separate from the Data Collection Forms. Coded data from the Data Collection Form will be collected and stored in a REDCap database. The ultrasound images from the sonoHSG will be stored in the research PACS.

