#### Part II: Data and Safety Monitoring Board or Committee

- When appropriate, attach a description of the DSMB.
- Provide the number of members and area of professional expertise.
- Provide confirmation that the members of the board are all independent of the study.

No data and safety monitoring board or committee is appointed because the study procedures are standard of care bearing minimum risk.

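### Assessing the side effects and difficulties of sonoHSG is a stated goal, but apart from pain the protocol requires nothing to be recorded separately for each procedure

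*Protocol*

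**What the plan says.** Section 4 of the protocol names six specific goals. One is "To assess the side effects and complications of and difficulties related to the procedure"; another is a safer infertility workup. Section 10 lists two endpoints: concordance (primary) and "Quantification of level of patient pain in regard to sonoHSG versus HSG" (secondary).

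Section 11 states that "subjects will have both the HSG and SonoHSG performed consecutively", in randomized order. The pain scale is given verbally straight after each one. The Schedule of Events then has one further contact, at 1-3 weeks: "Follow-up with subject via phone to assess any complications/infections".

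Under the data to be collected, section 11 says "The data collection form contains the following categories of information to be collected/obtained for each subject" and lists four: demographics, pre-existing conditions, the results of the two examinations, and the pain survey. Section 14 mentions adverse event logs and medical charts among the records that staff review. In section 15, Part I, the principal investigator reviews all adverse events for severity and for their relation to the study. Part II explains the absence of a monitoring board with "because the study procedures are standard of care bearing minimum risk".

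**The concern.** The goal concerns one procedure, and context makes that sonoHSG, the examination under evaluation. Every participant also undergoes HSG at the same visit. An event noticed afterwards can be assigned to sonoHSG only if someone recorded it at the time against the procedure during which it arose. The protocol does this for pain and for nothing else.

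At stake is the study's ability to say what sonoHSG costs the patient besides pain, and how often it is technically difficult or cannot be completed. Section 4 gives the overall aim as feasibility, and section 8 presents the pilot as the step before a larger trial, so these are facts the next study would want. A statistical analysis plan can specify tables, but it cannot recover observations that were never recorded.

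**Working it through.** The protocol gives no event rate or safety precision target, and section 8 says the sample size of 30 rests on feasibility. There is no planned figure to reproduce. The check compares what the goal needs with what each part of the protocol supplies.

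1. **Endpoint (section 10) and analysis (section 12).** Both cover concordance and pain. Neither mentions complications, other side effects or technical difficulty.
2. **Timing (section 11, Schedule of Events).** The complication call comes after both procedures. Randomizing the order does not help with a delayed event: whichever came first, the woman has had both by the time of the call. Infection, which section 17 names as a risk of sonoHSG, is an event of this kind.
3. **Data capture (section 11).** None of the four form categories is for side effects, complications, technical difficulty or the findings of the call. The results category might hold a note that an examination failed, but the protocol does not ask for one.
4. **Adverse event route (sections 14 and 15).** Logs and investigator review exist. The relation judged is to the study as a whole. No section requires a log entry to name the procedure.
5. **Incomplete procedures (section 16).** A woman who does not complete both procedures may be excluded from the analysis. An abandoned sonoHSG is the plainest example of a difficulty, yet she could leave the analysis with no required field saying why.
6. **What is captured by procedure.** Pain, immediately after each, with order and its interaction with procedure in the model (section 12).

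For scale only, the upper limit of the two-sided exact (Clopper-Pearson) 95% interval when no event is seen in n women is 1 − 0.025^(1/n).

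- n = 30 (all women, one observation each): 1 − 0.025^(1/30) = 11.6%.
- n = 15 (women having sonoHSG first): 1 − 0.025^(1/15) = 21.8%.
- At the enrolment ceiling of 50, with 25 per order: 1 − 0.025^(1/50) = 7.1% and 1 − 0.025^(1/25) = 13.7%.

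The groups of 15 and 25 assume equal allocation to the two orders, which the protocol does not state. Precision is modest either way. Recording by procedure gains attribution, because immediate events after the first procedure, noted before the second starts, cannot have been caused by the second.

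**The case against.** A reader might infer that the phone call is the sole route by which events are picked up. The documents do not support that. It is the only scheduled complication assessment, but section 14 refers to adverse event logs and charts, and section 15 has the principal investigator review every adverse event, after the first 10 subjects have completed follow-up and at least annually.

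A reader might also infer that nothing at all can be attributed to sonoHSG, or that the 10-subject review would have no data by procedure. That is too strong as well. Pain is scored after each procedure, and discomfort is among the risks listed in section 17. An acute event seen before the second procedure starts could be attributed if logged. A technical failure happens during one identifiable examination and could appear among the results or in the sonoHSG research report described in section 14.

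It can further be said that the protocol lists form categories rather than fields, that safety is not a named endpoint, and that infection cannot be attributed whatever form is used, because the concordance endpoint needs both examinations in every woman. The last point stands in full and limits what any fix can do. The second stands too: neither endpoint is affected. The first carries less weight, because the categories are stated and none of them is a natural place for side effects or the findings of the call.

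What survives is narrower than the strong readings: attribution is possible for some events, but it depends on someone choosing to record them by procedure.

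**Conclusion.** The concern holds in this limited form. Apart from pain, the protocol requires no capture by procedure of side effects, complications or difficulties, and provides no endpoint or form category for them. One of the six goals in section 4 therefore cannot be reliably met by following the plan as written.

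The size is that of an unserved goal; no estimate is biased. The confidence limits above only illustrate scale and do not measure the defect. The conclusion assumes that the procedure in the goal means sonoHSG, and that no case report form outside the protocol already holds the missing items. If such a form exists, the protocol should say so.

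A separate inconsistency lies in section 15, Part II, which calls the study procedures standard of care, while section 11 describes sonoHSG as performed for research. It does not bear on how events are captured, and this point takes no position on whether a monitoring board is needed.

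**What to change.** Add two items to the Data Collection Form and REDCap:

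- a short checklist of immediate side effects and of technical difficulty or an incomplete procedure, filled in with the pain score after each procedure and, for the first procedure, before the second starts;
- the findings of the follow-up call.

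Tabulate immediate events by procedure and by order, treating those after the first procedure as the uncontaminated comparison. Report delayed events as belonging to the combined visit, and state that they cannot be split by design.

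The cost is a few form fields and about a minute per procedure for staff already in the room giving the pain scale. No visit, procedure or person is added. The change has to be in place when each woman is seen, since the information cannot be rebuilt later.

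Separately, reconcile the description of the procedures in section 15, Part II with section 11.
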